### **Adverse Events of Interest**

Protocol prespecified AEs of interest included MACE, hypotension-related AEs, pancreatic events, calcitonin elevation, and thyroid neoplasm. Prior to study unblinding, additional AEs of interest were identified including nausea, vomiting, diarrhea, and AEs of injection site reaction. Since investigators may have reported the same clinical condition using different AE terms, prior to study unblinding a list of reported terms that are suggestive of the AEs of nausea, vomiting, diarrhea, injection site reactions, and pancreatic-related AEs was generated. These preferred terms were used to generate a combined analysis for each of these specific AEs of interest.

## **6.2. Clinical Laboratory Tests**

All clinical laboratory tests will be displayed for the subjects included in the safety analysis set. Laboratory data will be summarized for each type of laboratory test listed in [Attachment 1](#). Normal reference ranges for each test will also be provided.

Descriptive statistics will be presented for all chemistry, hematology, and urinalysis (pH and specific gravity) laboratory tests at scheduled time points. Descriptive statistics will be presented based on measurements on study medication, including up to a maximum of 14 days for JNJ-64565111 and placebo subjects, as well as all measurements regardless of the time of the last dose of double-blind study drug for subjects who discontinue from treatment before Week 12. Summaries based on both standard units (SI) and conventional units will be provided.

Change from baseline to scheduled time point as well as the 95% CI will be summarized for chemistry, hematology, and urinalysis (pH, and specific gravity) tests and displayed by visit and treatment group.

Number and percentage of subjects with postbaseline clinically important laboratory values will be presented and treatment group.

The percentage of subjects with specific treatment-emergent laboratory values meeting pre-defined limit of change (PDLC) criteria will be summarized for these laboratory analytes. The 95% CI for the percentage difference between the treatment groups will be provided for each treatment and combined JNJ-64565111 treatment group for the PDLC criterion which have at least 4 or more subjects in any treatment group; a corresponding listing will also be provided. The criteria for PDLC values are listed in [Attachment 2](#).

### 6.3. Vital Signs and Physical Examination Findings

Continuous vital sign parameters including pulse and blood pressure (systolic and diastolic) will be summarized at each assessment time point. Changes from baseline will be summarized for the 12-week treatment phase. Descriptive statistics (mean, standard deviation, median, interquartile range [IQR], minimum and maximum) will be presented at each scheduled time point, including the 95% CI for the change from baseline for the 12-week treatment phase. The descriptive statistics will be presented based on measurements on study medication, including up to a maximum of 14 days for JNJ-64565111 and placebo subjects, as well as all measurements regardless of the time of the last dose for subjects who discontinue from treatment before Week 12. The pulse and blood pressure measurements will be based on the average of the consecutive sitting pulse and blood pressure readings that were collected at each visit.

The percentage of subjects with specific treatment-emergent vital sign values meeting PDLC criteria ([Attachment 2](#)) will be summarized for these vital sign parameters. The 95% CI for the percentage difference between the treatment groups will be provided for each treatment and combined JNJ-64565111 treatment group for the PDLC criterion which have at least 4 or more subjects in any treatment group; a corresponding listing will also be provided.

Physical examination findings will not be summarized except when reported as an adverse event.

### 6.4. Electrocardiogram

A 12-lead ECG will be performed during screening. No summary is planned.

## 7. PHARMACOKINETICS/IMMUNOGENICITY/PHARMACODYNAMICS

### 7.1. Pharmacokinetics

Pharmacokinetics (PK) samples for measuring serum JNJ-64565111 concentrations will be collected from all subjects at the specified visits as shown in the schedule of events of the protocol. In all subjects randomly assigned to JNJ-64565111 or matching placebo, venous blood samples will be collected according to the Time and Events Schedule for determination of serum trough concentrations of JNJ-64565111 to assess attainment of steady state concentrations. In addition, a sample at the 4-week safety follow-up visit will also be collected in all subjects. On the days of the trough clinic visits at which PK samples are to be obtained, subjects are not to inject the study drug before arriving at the clinic. In addition to the trough samples and a post-treatment sample in all subjects, all subjects will have 1 additional visit (Day 4 ± 1 day sampling window) to collect a non-trough PK sample. All PK evaluations will be based on the PK analysis set. No imputation for missing concentration data will be performed.

The data analysis of trough and non-trough serum JNJ-64565111 concentrations includes the following:

- Tabular summary of serum JNJ-64565111 concentrations at each PK visit by treatment group.

- Tabular summary of serum JNJ-64565111 concentrations at each visit by treatment group and body weight tertiles at baseline.
- Proportion of subjects without detectable serum JNJ-64565111 concentration at each visit by treatment group.
- Median trough, non-trough, and week 16 temporal serum JNJ-64565111 concentrations plotted over time by treatment group.
- Median trough serum JNJ-64565111 concentrations plotted over time by treatment group to assess attainment of steady-state.

In addition, the relationship between serum JNJ-64565111 concentrations, and antibody to JNJ-64565111 status, safety and efficacy may be explored using graphical displays.  $\geq 5\%$  and  $\geq 10\%$  weight loss response rates and % weight loss at Week 12 will be presented in a bar graph by the corresponding serum JNJ-64565111 concentration quartiles at Week 12 for subjects treated with JNJ-64565111.

For summary statistics of serum JNJ-64565111 concentrations, concentration values below the lower limit of quantification will be treated as zero. Once a subject meets one of the following dosing deviation criteria, the subject's data will be excluded from the by-visit data analyses from that point onwards.

Dosing deviation criteria:

- Discontinued SC study agent administrations.
- Skipped a SC administration.
- Received an incomplete/ incorrect SC dose.
- Received an incorrect SC study agent.
- Received an additional SC dose.

In addition, if a subject has an administration more than 4 days earlier or later than the scheduled dosing date, the concentration data collected between such a dosing visit and the subsequent dosing visit will be excluded from the by-visit data analyses. For the Week 12 visit, if the PK sampling time deviates more than 4 days earlier or later than the scheduled date, the PK concentration at this visit will be excluded from the by-visit data analyses.

The conditions under which to exclude measurements from PK analysis:

- If date/time of Baseline sample is after date/time of first dose, then exclude the Baseline sample
- If Day 4 sample is  $>8$  days after 1st dose, then exclude the Day 4 sample
- If date of Week 2 sample – date of previous dose before date of Week 2 sample is  $< 3$  days or  $> 11$  days, then exclude Week 2 sample
- If date of Week 6 sample – date of previous dose before date of Week 6 sample is  $< 3$  days or  $> 11$  days, then exclude Week 6 sample

- If relative Study Day of Week 12 sample is < Day 80 or >Day 88 then exclude Week 12 sample
- If relative Study Day of Week 16 sample is < Day 108 or >Day 116 then exclude Week 16 sample
- If subject discontinues treatment early, then exclude the “Week 16” or “4 Week Follow-up” PK sample.

Population PK analyses will be performed to characterize the population PK parameters based on the available JNJ-64565111 concentration data obtained through the Week 16 visit. Sparse PK data from the current study may be pooled with previous Phase 1 data with rich PK profiles to allow estimation of structural PK parameters. The population pharmacokinetic approach will also be used to identify and quantify any significant covariates such as demographic characteristics (including but not limited to body weight, ethnic origin, sex, and age) and concomitant medications that have substantial impact on the population pharmacokinetics of JNJ-64565111 in subjects with severe obesity. A detailed analysis plan for population PK analysis will be developed separately, and a stand-alone technical report will be written to summarize the results of the population PK analysis.

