4. STUDY DESIGN

4.1. Overall Design

This is a randomized, double-blind, placebo-controlled, parallel-group, 4-arm, multicenter study in severely obese subjects with T2DM. Subjects who are ≥ 18 and ≤ 70 years of age and have a BMI ≥ 35 kg/m² to ≤ 50 kg/m² are eligible to participate if they have a HbA_{1c} of $\geq 6.5\%$ to $\leq 9.5\%$ at the screening visit on diet and exercise alone or on a stable dose of single oral AHA or dual-combination oral AHAs for ≥ 12 weeks prior to screening. A target of 188 subjects will be randomly assigned in this study.

Subjects meeting all enrollment criteria will enter a 2-week run-in phase, which is to occur approximately 1 week after the screening visit and is designed to train the subject on SC self-injection and to establish the subject's ability to comply with the protocol-specified requirements. On Day 1, subjects who continue to meet eligibility criteria, will be randomly assigned in a 1:1:1:1 ratio to blinded treatment with placebo or JNJ-64565111 5.0 mg, 7.4 mg, or 10 mg and enter a 12-week treatment phase. Post-randomization visits will be conducted at Week 2, 6, 12/end-of-treatment [EOT] visit, and the SAE follow-up visit 5 weeks after the last dose of study drug. At Weeks 4 and 10, all subjects will be contacted preferably by telephone to reinforce the adherence to diet and exercise, study drug dosing reminder, assessment of subjects' status, and compliance with the protocol procedures (eg, diary completion reminder).

During the pretreatment/run-in and treatment phases, subjects will undergo efficacy and safety assessments including physical examination, ECG, laboratory testing and vital signs measurement. A serum pregnancy test will be performed at screening and Week 12/EOT along with a urine pregnancy test at Day 1 in women of childbearing potential.

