6.7. Dose Modification

JNJ-64565111 or matching placebo will not be titrated. Subjects will self-administer the full dose of JNJ-64565111 or matching placebo on Day 1 and will remain on their assigned dosages throughout the treatment phase (ie, until Week 12 or early discontinuation of study drug).

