### 5.2.3. Analysis Methods

#### Primary Analysis

The primary efficacy endpoint will be analyzed based on the mITT analysis set using a mixed model for repeated measures (MMRM). The analysis will use the observed data through Week 12 while on treatment (up to the last dose of study drug plus 14 days). The analysis model will include the fixed, categorical effects of treatment, visit, and treatment-by-visit interaction, as well as the continuous covariates of baseline body weight and baseline-by-visit interaction. An unstructured covariance will be used to model the within-patient errors. The treatment comparisons will be made between each of the JNJ-64565111 treatment groups and placebo at Week 12 based on this model.

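### The SAP's graph of weight loss by Week 12 concentration quartile is unadjusted for baseline weight, so its gradient is confounded if weight affects both exposure and percentage loss

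*SAP*

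**What the plan says.** - **The display.** SAP 7.1 takes the two response rates and the percentage weight loss, all measured at the end of treatment, and states that they "will be presented in a bar graph by the corresponding serum JNJ-64565111 concentration quartiles at Week 12". The display is restricted to those given the active drug. It names no covariate and no stratification by dose or weight. The planned concentration summaries listed just before it are all by treatment group. This display is not so described, so quartiles pooled over the three active doses are the natural reading, though not an explicit statement.
- **Dosing.** Protocol 4.1 randomises subjects in a "1:1:1:1 ratio to blinded treatment with placebo or JNJ-64565111 5.0 mg, 7.4 mg, or 10 mg". Under Protocol 6.7 there is no titration and subjects "will remain on their assigned dosages throughout the treatment phase".
- **Weight and exposure.** SAP 7.1 also plans a "Tabular summary of serum JNJ-64565111 concentrations at each visit by treatment group and body weight tertiles at baseline". Its population PK covariates are described as "including but not limited to body weight, ethnic origin, sex, and age". Both concern weight and concentration, not response.
- **Weight and response.** The primary model in SAP 5.2.3 includes "the continuous covariates of baseline body weight". The logistic model for ≥5% loss in SAP 5.3.2 also has baseline weight as a covariate, and SAP 5.4.2 uses a similar model for the categorical exploratory endpoints, which include ≥10% loss.
- **Other exposure-response work.** SAP 7.3 and Protocol 9.4.3 make it optional and specify no baseline-weight adjustment of response.

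**The concern.** Dose is randomised, but observed concentration within a dose is not. With a fixed dose, a lighter subject may reach a higher concentration. If lighter subjects also lose a different percentage of weight for reasons unrelated to the drug level, the top and bottom quartiles differ in body size as well as exposure, and the bars show the sum of the two effects. The gradient could then suggest an exposure-response that is absent or flatten one that is real.

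All three outcomes on the graph are adjusted for baseline weight elsewhere in the SAP. The adjustment is missing from the one committed display of them in which the groups are not formed by randomisation. At stake is the reading of an exploratory figure in a trial that Protocol 2.1 says can inform Phase 3 dose selection.

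**Working it through.** **The plan's own figure.** No size or precision is stated for this graph. The only relevant planning figures are in SAP 1.4: SD 4%, difference 2.7%, 47 per group, about 90% power. These reproduce for one pairwise comparison at two-sided 0.05: 2.7 / (4 × √(2/47)) = 3.27, and Φ(3.27 − 1.96) = 90.5%. Only the SD of 4 is used below.

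**Inputs from the documents**
- Active subjects: 3 × 47 = 141, so about 35 per quartile.
- Doses 5, 7.4 and 10 mg in equal numbers. The variance of log dose is 0.0805.
- Spread of exposure within a dose, from the Cmax values in Protocol 2.2: 0.072/0.259 = 28%, 0.22/0.744 = 30%, 0.20/0.565 = 35%, 0.66/2.14 = 31%. These are first- and fourth-dose Cmax values, not Week 12 troughs. Residual log-SDs of 0.3 and 0.4 are used.

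**Assumptions not in the documents**
- Log-SD of baseline weight: 0.17.
- Slope k of log concentration on log weight: 0.5 to 0.9, with concentration falling as weight rises.
- Correlation r of baseline weight with percentage weight loss: −0.3 to 0.3, including 0.

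**Formula.** Let D be the gap in mean baseline weight, in SD units, between bottom and top quartile. With no true concentration effect,

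bias (top minus bottom) = −r × 4 × D.

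D comes from the correlation of log concentration with weight. For k = 0.9 and residual 0.3, the weight term is 0.9 × 0.17 = 0.153 and the total log variance is 0.0805 + 0.153² + 0.3² = 0.194. The correlation is therefore −0.153/√0.194 = −0.347, and simulation gives D = 0.87.

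| k | Residual log-SD | D | Size of bias, \|r\| = 0.1 | 0.2 | 0.3 |
|---|---|---|---|---|---|
| 0.5 | 0.3 | 0.51 | 0.20 | 0.41 | 0.61 |
| 0.5 | 0.4 | 0.43 | 0.17 | 0.34 | 0.52 |
| 0.75 | 0.3 | 0.74 | 0.30 | 0.59 | 0.89 |
| 0.75 | 0.4 | 0.63 | 0.25 | 0.50 | 0.76 |
| 0.9 | 0.3 | 0.87 | 0.35 | 0.70 | 1.04 |
| 0.9 | 0.4 | 0.75 | 0.30 | 0.60 | 0.90 |

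At r = 0 the bias is 0. It is positive for negative r and negative for positive r. With baseline weight as a covariate, the simulated top-minus-bottom difference is 0 to within about 0.02 in every setting.

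**With a true effect.** Assume 1 point of loss per doubling of concentration, k = 0.75 and total within-dose log-SD 0.35. The adjusted contrast is about 1.6. The unadjusted contrast is 0.8 at r = 0.3 and 2.5 at r = −0.3.

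**Precision.** The standard error of the top-minus-bottom contrast is 4 × √(2/35) = 0.96. The PK exclusions in SAP 7.1 can only reduce the number per quartile.

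**Within-dose quartiles.** Forming quartiles inside each dose removes the randomised part of the concentration spread, so weight explains more of what remains. At k = 0.9, D rises from 0.87 to 1.16 (residual 0.3) and from 0.75 to 0.91 (residual 0.4). At |r| = 0.3 the unadjusted bias rises from 1.04 to 1.39 and from 0.90 to 1.09.

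These calculations cover percentage weight loss only. No size was derived for the two response rates, to which the same reasoning applies.

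**The case against.** **The bias needs two relations that the documents do not quantify.** This stands. Including baseline weight in the efficacy model is not an estimate of its correlation with percentage loss, and at r = 0 there is nothing to correct.

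**A reader might infer that the SAP expects lighter subjects to have higher concentrations.** It does not say so. A tertile table and a list of PK covariates show that the question will be examined, not what the answer is. Protocol 4.3 also reports overall similar variability in exposure under fixed and weight-based dosing at the 5 and 10 mg equivalents. That tempers the concern without removing it. With k = 0.75, weight log-SD 0.17 and residual log-SD 0.30, the total log-SD would be √(0.30² + 0.1275²) = 0.33 under fixed dosing and √(0.30² + 0.0425²) = 0.30 under weight-based dosing. Phase 1 fixed-dose groups with 8 active subjects each (Protocol 2.2) could not separate these.

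**A reader might infer that the graph could misdirect the Phase 3 dose.** The documents do not support that. The randomised dose-versus-placebo comparisons adjust for baseline weight and carry Hochberg control, and MCP-Mod addresses dose-response. The graph carries no test. Nor should the bias be measured against the 2.7-point design difference, which is an active-versus-placebo contrast.

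**Other parts of the plan may cover the point.** The tertile table would reveal a weight-exposure link, but neither it nor the population PK analysis adjusts the response shown on the graph. The figure layouts are in the Data Presentation Specifications (SAP 1), which were not available, so pooling over doses remains an inference.

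**Conclusion.** The point holds as a minor one. The planned quartile graph is unadjusted for baseline weight, and its gradient is confounded if weight affects both Week 12 concentration and percentage weight loss. Under the assumed ranges the bias in the top-minus-bottom contrast runs from 0 to about 1.0 percentage point in either direction, at most about one standard error (0.96). It is exactly zero if either relation is absent. The primary analysis, the secondary endpoints and the randomised dose comparisons are unaffected. Adjusting for weight would remove this one source of confounding but would not make observed concentration a randomised exposure.

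**What to change.** Add a sentence to SAP 7.1:

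- Keep the raw bars if wanted. Beside them, show quartile means of percentage weight loss from an ANCOVA with concentration quartile as factor and baseline body weight as covariate.
- Show the ≥5% and ≥10% response rates by quartile from the logistic model with baseline weight that the SAP already uses, with quartile in place of treatment.
- State the dose mix of each quartile.
- Label the display descriptive and non-randomised.

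Do not substitute unadjusted within-dose quartiles, because they enlarge the weight bias.

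The cost is one SAP sentence and one extra program. Baseline weight is already collected, so no new data are needed.

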On Day 1, subjects randomly assigned to the double-blind treatment arms will receive a supply of their randomly-assigned study drug and will be reminded of the once weekly dosing regimen and to record the date and time of each administered dose in the study drug diary. Subjects will self-administer the first dose of JNJ-64565111 or matching placebo at the site under the supervision of study staff.

Drug Administration

Subjects will be instructed to administer study drug SC once weekly for the entire duration of the 12-week treatment phase or until early discontinuation.

Subjects will be instructed to inject to the 4 quadrants of the anterior abdominal wall. For consistency, and to avoid dosing in the same abdominal area, subjects should be instructed to begin in one quadrant and on subsequent dosing days proceed in the next quadrant in a counterclockwise manner.

Injections can be done at any time of day irrespective of meals. However, it is preferable that study drug be injected during the same overall time period of the day on a week-to-week basis.

Study drug should be taken on the same day of the week throughout the study (ie, the regularly scheduled study drug day).

[figure not shown]
If the day of the once weekly injection coincides with the day of a clinic visit, subjects are NOT to inject JNJ-64565111 or matching placebo before arriving at the clinic. Instead, AFTER all study visit procedures have been completed, subjects may self-administer blinded study drug either at the study site or once they have returned home.

Subjects are to record the date and time of study drug administration on the study drug diary, and should mark a calendar to remind them of when to take the next weekly dose. Subjects will be instructed to record the date and time of each self-injection throughout the run-in and treatment phase which allows an assessment of treatment compliance and the relationship of PK measurements and safety assessments to the time of study-drug dosing. The information will be entered into eCRFs by the site personnel.

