Subjects should be instructed not to take 2 doses within 3 days (72 hours) of each other. If a subject misses taking the next dose of study drug on their regularly scheduled study drug day, the missed dose should be taken as soon as possible, if there are at least 3 days (72 hours) until their next regularly scheduled study drug day. If there are less than 3 days remaining, the subject should skip the missed dose and take the next dose on their regularly scheduled study drug day.

Study-site personnel will instruct subjects on how to store study drug for at-home use as indicated for this protocol. Figure 3 is a schematic diagram of the study drug injection schedule.

Figure 3: Schematic Diagram of Drug Injection Schedule

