8.5. Pharmacokinetics

Serum samples will be used to evaluate the PK of JNJ-64565111. Serum collected for PK may additionally be used to evaluate safety or efficacy aspects that address concerns arising during or after the study period. Genetic analyses will not be performed on these serum samples. Subject confidentiality will be maintained.

Evaluations

Refer to the Schedule of Activities for the timing and frequency of all sample collections.

Blood collections for PK assessments should be kept as close to the specified time as possible.

Venous blood samples will be collected from all subjects according to the Schedule of Activities for determination of serum trough concentrations of JNJ-64565111 to assess attainment of steady-state concentrations. In addition, a non-trough (peak) sample on Day 4 will be collected from all subjects, as well as a post-treatment sample at 16 weeks from all subjects. On the days of the trough clinic visits at which PK samples are to be obtained, subjects are not to inject the study drug before arriving at the clinic.

The non-trough PK sampling time point was prospectively optimized for population-based PK analyses. In addition to the trough samples and a post-treatment sample in all subjects, all subjects will have 1 additional visit (Day 4±1-day sampling window) to collect a non-trough PK sample.

The exact dates and times of previous study drug injection and blood sampling for PK must be recorded in the eCRF or laboratory requisition form for all PK samples.

See the laboratory manual for information regarding handling of biologic samples.

Pharmacokinetic Analytical Procedures

Serum samples will be analyzed to determine concentrations of JNJ-64565111 using a validated, specific, and sensitive immunoassay method by or under the supervision of the sponsor.

Parameters

Serum concentrations at each time point of measurement will be evaluated by descriptive statistics, including arithmetic mean, geometric mean, standard deviation, coefficient of variation, geometric coefficient of variation, minimum, maximum, and median.

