### 2.4. Study Day and Relative Day

“Study Day 1” or “Day 1” refers to the day of the first study agent administration on or after the randomization date. All efficacy and safety assessments at all visits will be assigned a day relative to this date.

Study day or relative day for a visit is defined as:

- Visit date - (date of Study Day 1) +1, if visit date is ≥ date of Day 1
- Visit date - Date of Day 1, if visit date < date of Day 1

There is no 'Day 0'.

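### SAP 7.1 does not require the Day 4 PK sample to precede dose 2, so a late post-dose-2 draw could be summarised as the first-dose non-trough level

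*SAP*

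**What the plan says.** Protocol 8.5 states that "a non-trough (peak) sample on Day 4 will be collected from all subjects" and gives its timing: "all subjects will have 1 additional visit (Day 4±1-day sampling window) to collect a non-trough PK sample". SAP 7.1 repeats the same ± 1 day window.

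The SAP 7.1 list of conditions for leaving out PK measurements sets a different limit for this sample: "If Day 4 sample is $>8$ days after" the first "dose, then exclude the Day 4 sample". The rule has an upper limit only and does not mention dose 2. The Week 2 and Week 6 rules in the same list are two-sided (3 to 11 days) and are counted from the previous dose.

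On dosing, Protocol 6.1 says: "Subjects will be instructed to administer study drug SC once weekly". It also says: "Subjects should be instructed not to take 2 doses within 3 days (72 hours) of each other". SAP 2.4 numbers days from the first dose as "Visit date - (date of Study Day 1) +1", so Study Day d is d − 1 days after dose 1.

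SAP 7.1 lists the outputs that use the sample: concentration tables by visit and treatment group, the same by baseline body-weight tertile, the proportion without detectable drug at each visit, and a median plot of trough, non-trough and Week 16 concentrations.

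**The concern.** The Day 4 draw is the only scheduled on-treatment sample not taken at trough, and it is meant to describe the level after a single dose. The retained range runs past the time when dose 2 is due. A sample taken after dose 2 carries the contribution of two injections, yet it would appear in the Day 4 row and at the Day 4 point of the median plot. A reader comparing dose groups on first-dose exposure would have no sign that some values reflect two doses.

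**Working it through.** **Day arithmetic (SAP 2.4, SAP 7.1, Protocol 6.1)**

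- Planned window: Study Days 3 to 5, which is 2 to 4 days after dose 1.
- Retained by the exclusion rule: up to 8 days after dose 1, which is Study Day 8 + 1 = 9.
- Dose 2 due: 7 days after dose 1, which is Study Day 8.
- Overlap: a draw between 7 and 8 days after dose 1 is kept and may follow an on-time dose 2.
- If the 8 was meant as Study Day 8, a draw later on Study Day 8 than the injection would still be kept.

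**Do the other SAP 7.1 exclusions catch it?** They cover discontinuation; a skipped, incomplete, incorrect or additional dose; the wrong agent; and a dose more than 4 days off schedule. An on-time dose 2 followed by a late Day 4 draw meets none of these. An early dose 2 can also pass: taken 3 days after dose 1, it is 7 − 3 = 4 days early. That is not more than 4, and it sits at the limit of the protocol's minimum gap.

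**Size (illustration)**

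The model form is an assumption: one compartment, first-order absorption, doses added by superposition. Inputs from the documents are a half-life of 6 to 8 days (Protocol 4.3) and a first-dose Tmax of 2 to 7 days (Protocol 2.2, fixed-dose study). Tmax was run from 2 to 6 days, so the top of that range is not covered.

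- ke = ln 2 / half-life; ka solves Tmax = ln(ka/ke)/(ka − ke).
- C(t) is proportional to exp(−ke·t) − exp(−ka·t).
- Ratio for a sample at 8 days with dose 2 at day 7: [C(8) + C(1)] / C(3).

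Worked case, half-life 7 days and Tmax 4 days: ke = 0.099, ka = 0.508.

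- C(3) = 0.743 − 0.218 = 0.525
- C(8) = 0.453 − 0.017 = 0.436
- C(1) = 0.906 − 0.602 = 0.304
- Ratio = (0.436 + 0.304)/0.525 = 1.41

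Over the whole grid, relative to 3 days after dose 1:

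| Sample | Ratio |
|---|---|
| 8 days, dose 2 at day 7 | 1.35 to 1.63 |
| 8 days, dose 2 at day 4 (early) | 1.48 to 2.28 |
| 7 days, before dose 2 | 0.65 to 1.19 |

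Both post-dose-2 rows exceed 1 in every case run. The pre-dose-2 row spans 1.

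**Check on the pre-dose-2 case from the protocol's own data.** Week 1 average concentration divided by Cmax (Protocol Table 2, AUC/168/Cmax):

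- 5 mg: 34.4/168/0.259 = 0.79
- 10 mg: 81.8/168/0.613 = 0.79
- 12.4 mg: 46.7/168/0.363 = 0.77
- 15 mg: 93.6/168/0.744 = 0.75

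The first-week profile is fairly flat, so a late draw before dose 2 need not be far from the peak.

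**The case against.** A collection window and an exclusion tolerance serve different purposes. Day 4 ± 1 tells sites when to draw; the SAP list says when a late draw is dropped. Most limits in that list are target ± 4 days (7 ± 4 = 3 to 11, 84 ± 4 = 80 to 88, 112 ± 4 = 108 to 116), and 4 + 4 = 8 fits, although the SAP does not give this reason. This stands: keeping samples outside Days 3 to 5 is not in itself a contradiction.

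The exposure is also narrow. With dose 2 on time, the draw must be at least 7 − 4 = 3 days past the window. Protocol 6.1 tells subjects not to inject before arriving when injection day and clinic day coincide, so a Study Day 8 draw should precede dose 2 if the instruction is followed. That leaves mainly Study Day 9 draws and early second doses. Medians are little moved by a few such values.

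Nothing decisive rests on this row. The time point was chosen for population PK, exact dosing and sampling times are recorded, steady state is judged from the trough-only plot, and the weight-loss bar graph uses Week 12 concentrations. Protocol 9.4.3 also allows subjects to be left out when their data do not permit accurate PK assessment, but that is a general provision and does not name this case.

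These arguments limit the effect. They do not supply the missing condition on dose 2.

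**Conclusion.** The gap is real but minor. As written, the rule allows a Day 4 sample drawn after dose 2 to be reported as a first-dose non-trough level, and no other listed exclusion prevents it when dose 2 is on time. An affected sample at 8 days would read about 1.35 to 1.63 times the level 3 days after dose 1. That figure rests on the assumed one-compartment model with half-life 6 to 8 days, Tmax 2 to 6 days and dose 2 at day 7. How many samples would be affected cannot be learned from the documents; it is probably few. The effect is confined to descriptive PK tables and plots. The efficacy analyses are untouched, and a population PK model using actual times would be largely unaffected.

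A reader might go further and infer that every draw beyond Day 5 is contaminated, or that a trough-time draw before dose 2 distorts the summary. The documents do not support that: first-dose Tmax is 2 to 7 days, and the day-7 pre-dose ratio of 0.65 to 1.19 has no fixed direction. Cutting the tolerance to Days 3 to 5 would be a preference, not a correction.

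**What to change.** Add one condition to the Day 4 line in SAP 7.1: the sample is also excluded from the by-visit summaries and plots if its recorded date and time fall after the second dose. Say explicitly that this applies to the descriptive outputs only, because the list is introduced as covering PK analysis in general. The sample should stay in the population PK analysis with its actual dosing and sampling times.

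The cost is one SAP line and a check against dose dates and times that Protocol 8.5 already requires to be recorded. The downside is that a few late samples leave the descriptive summary.
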